7.3. Blinding

This is a double-blind study. After database lock of trials JAHZ and JAIA, site personnel and patients will remain blinded to treatment assignment.

In case of an emergency, the investigator has the sole responsibility for determining if unblinding of a patient's treatment assignment is warranted. Patient safety must always be the first consideration in making such a determination. If the investigator decides that unblinding is warranted, the investigator should make every effort to contact the sponsor-designated medical monitor prior to unblinding a patient's treatment assignment, unless this could delay emergency treatment of the patient. If a patient's treatment assignment is unblinded, Lilly must be notified immediately.

Emergency unblinding for AEs may be performed through the IWRS. This option may be used ONLY if the patient's well-being requires knowledge of the patient's treatment assignment. All calls resulting in an unblinding event are recorded and reported by the IWRS.

If an investigator, site personnel performing assessments, or patient is unblinded, the patient must be discontinued from the study. In cases where there are ethical reasons to have the patient remain in the study, the investigator must obtain specific approval from a Lilly-designated medical monitor for the patient to continue in the study.

7.4. Dosage Modification

During this study, treatment assignment and dose adjustment of investigational product will be followed strictly as indicated in Section 7.2.1 and Section 7.2.2.

If, after final analysis of the SLE Phase 3 originating studies, it is determined that either dose of baricitinib does not have a positive benefit/risk profile, then that dose arm may be discontinued and all patients transferred to the remaining dose arm. This modification would be made via an amendment to this protocol.

See Section 7.7 for permitted concomitant therapy.

7.5. Preparation/Handling/Storage/Accountability

All investigational product (used and partially used) will be returned to the sponsor or destroyed at the site with the sponsor's written approval. In some cases, sites may destroy the material if, during the investigative site selection, the evaluator has verified and documented that the site has appropriate facilities and written procedures to dispose of clinical trial materials.

Storage and handling instructions are provided on the investigational product packaging and should be followed.

7.6. Treatment Compliance

Patient compliance with investigational product will be assessed at each visit and at Early Termination during the treatment period by counting returned tablets. Deviations from the prescribed dosage regimen should be recorded in the electronic case report form (eCRF).

A patient will be considered significantly noncompliant if he or she misses >20% of the prescribed doses during the treatment period, unless the patient's investigational product was withheld by the investigator for safety reasons.

Similarly, a patient will be considered significantly noncompliant if he or she is judged by the investigator to have intentionally or repeatedly taken more than the prescribed amount of investigational product. Patients found to be noncompliant with the investigational product should be assessed to determine the reason for noncompliance and educated and/or managed as deemed appropriate by the investigator to improve compliance.

7.7. Concomitant Therapy

Patients may continue to receive the background standard therapies for SLE they were receiving at completion of the originating study. Changes in dose of background standard therapies for SLE, such as an increase in dose of antimalarials or immunosuppressants, are permitted during the study. Initiation of new antimalarials or immunosuppressants are prohibited during the study.

In addition, changes in concomitant medication, such as an increase in corticosteroids to manage any increase in disease activity or corticosteroid tapering, are permitted during the study in accordance with long term management of disease activity and at the investigator's discretion. Any required corticosteroid bursts should be aligned with clinical practice.

Prohibited concomitant treatments include those outlined in the exclusion criteria of the originating trials.

- Scheduled parenteral corticosteroids, biologic treatments for immunologic disease, cyclophosphamide, belimumab, anifrolumab (or any other anti-IFN therapy), rituximab, any other B cell depleting therapies, intravenous immunoglobulin or any other JAK inhibitors.

Any changes to the patient's medication must be discussed with the investigator. Patients should be instructed to consult the investigator or other appropriate study personnel at the site before taking any new medications or supplements.

Additional medications are to be avoided during the study unless required to treat an AE or for the treatment of an ongoing medical problem.

Any additional medication, whether prescription or over-the-counter, used at baseline and/or during the course of the study must be documented in the eCRF with start and stop dates.

7.8. Treatment after the End of the Study

7.8.1. Treatment after Study Completion

Baricitinib will be made available to patients until the conclusion of the study. Patients will be referred to their local treatment centers for continued therapy as clinically indicated.

8. Discontinuation Criteria

8.1. Discontinuation from Study Treatment

8.1.1. Temporary Interruption of Investigational Product

In some circumstances, it may be necessary to temporarily interrupt treatment as a result of AEs or abnormal laboratory values that may have an unclear relationship to investigational product. It is recommended that the investigator consult with Lilly (or its designee) before temporarily interrupting therapy for reasons other than those defined in [Table JAIM.4](#). Retest timing and frequency is at the investigator's discretion.

Investigational product that was temporarily interrupted because of an AE or abnormal laboratory value, not specifically covered in [Table JAIM.4](#), may be restarted at the discretion of the investigator. Investigational product must be held in the following situations and may only be resumed as noted in the table.

Table JAIM.4. Criteria for Temporary Interruption of Investigational Product

Hold Investigational Product if the Following Abnormalities Occur:	Investigational Product May be Resumed When:
WBC count <2000 cells/ μ L ($<2.00 \times 10^3/\mu$ L or <2.00 GI/L)	WBC count ≥ 2500 cells/ μ L ($\geq 2.50 \times 10^3/\mu$ L or ≥ 2.50 GI/L)
ANC <1000 cells/ μ L ($<1.00 \times 10^3/\mu$ L or <1.00 GI/L)	ANC ≥ 1200 cells/ μ L ($\geq 1.2 \times 10^3/\mu$ L or ≥ 1.2 GI/L)
Lymphocyte count <300 cells/ μ L ($<0.30 \times 10^3/\mu$ L or <0.30 GI/L)	Lymphocyte count ≥ 500 cells/ μ L ($\geq 0.50 \times 10^3/\mu$ L or ≥ 0.50 GI/L)
Platelet count <25,000/ μ L ($<25 \times 10^3/\mu$ L or <25 GI/L)	Platelet count $\geq 50,000/\mu$ L ($\geq 50 \times 10^3/\mu$ L or ≥ 50 GI/L)
eGFR <40 mL/min/1.73 m ² for patients with eGFR ≥ 60 mL/min/1.73 m ²	eGFR ≥ 50 mL/min/1.73 m ²
ALT or AST >5 x ULN	ALT and AST return to <2 x ULN and possible DILI has been ruled out, and IP is not considered to be the cause of enzyme elevation
Hemoglobin <8 g/dL (<80.0 g/L)	Hemoglobin ≥ 9 g/dL (≥ 90.0 g/L)
Symptomatic herpes zoster	All skin lesions have crusted and are resolving
Infection that, in the opinion of the investigator, merits the IP being withheld ^a	Resolution of infection that, in the opinion of the investigator, merits the IP being restarted

Abbreviations: ALT = alanine aminotransferase; ANC = absolute neutrophil count; AST = aspartate aminotransferase; eGFR = estimated glomerular filtration rate; IP = investigational product; ULN = upper limit of normal; WBC = white blood cell.

^a Permanent discontinuation of IP should be considered for patients who develop a serious infection that, in the opinion of the investigator, would pose an unacceptable risk if IP were resumed.

8.1.2. **Permanent Discontinuation from Study Treatment**

Possible reasons leading to permanent discontinuation of investigational product:

- **Subject Decision**
 - The patient requests to discontinue investigational product.
- **Investigator Decision**
 - The investigator decides that the patient should be discontinued from investigational product.
- **Discontinuation due to a hepatic event or liver test abnormality.** Patients who are discontinued from investigational product due to a hepatic event or liver test abnormality should have additional hepatic safety data collected via eCRF.

Discontinuation of the investigational product for abnormal liver tests **should be** considered by the investigator when a patient meets one of the following conditions after consultation with the Lilly-designated medical monitor:

- ALT or AST >8 x upper limit of normal (ULN)
- ALT or AST >5 x ULN for more than 2 weeks after temporary interruption of investigational product
- ALT or AST >3 x ULN and either total bilirubin level (TBL) >2 x ULN or international normalized ratio >1.5
- ALT or AST >3 x ULN, with the appearance of fatigue, nausea, vomiting, right upper-quadrant pain or tenderness, fever, rash, and/or eosinophilia (>5%)
- Alkaline phosphatase (ALP) >3 x ULN
- ALP >2.5 x ULN and TBL >2 x ULN
- ALP >2.5 x ULN, with the appearance of fatigue, nausea, vomiting, right quadrant pain or tenderness, fever, rash, and/or eosinophilia (>5%)
- **Discontinuation due to Other Laboratory Abnormalities:**
 - White blood cell count <1000 cells/ μ L (1.00x10³/ μ L or 1.00 GI/L)
 - Absolute neutrophil count <500 cells/ μ L (0.50x10³/ μ L or 0.50 GI/L)
 - Lymphocyte count <200 cells/ μ L (0.20x10³/ μ L or 0.20 GI/L)
 - Hemoglobin <6.5 g/dL (<65.0 g/L)

Temporary interruption rules (see Section 8.1.1) must be followed where applicable. For lab values that meet permanent discontinuation thresholds, investigational product should be discontinued. However, if in the opinion of the investigator, the lab abnormality is due to intercurrent illness or another identified factor, lab tests may be repeated. The investigator may be able to restart investigational product after consultation with the Lilly-designated medical

monitor, only when the lab value meets resumption thresholds (Table JAIM.4) following the resolution of the intercurrent illness or other identified factor.

- **Discontinuations due to other circumstances:**
 - Pregnancy
 - Malignancy (except for successfully treated basal cell or squamous epithelial skin cancers)
 - Hepatitis B virus DNA is detected with a value above the lower limit of quantitation (see Section 9.4.6).
 - Occurrence of a VTE (DVT/pulmonary embolism [PE]) during the study
 - Serious infection, that in the opinion of the investigator merits the investigational product being discontinued
 - If the patient, for any reason, requires treatment with another therapeutic agent that may be effective for treatment of SLE that is noncompliant to the concomitant therapy requirements (see Section 7.7) during the study. Discontinuation from the investigational product must occur prior to introduction of the new agent.

Throughout the trial, investigators should continue to assess benefit-risk for patients to remain in the trial, and should consider discontinuing patients if sufficient clinical benefit is not observed with protocol allowed treatments.

Patients discontinuing from study treatment prematurely for any reason, should complete AE and other safety follow-up per Section 2 (Schedule of Activities), Section 9.2 (Adverse Events), and Section 9.4 (Safety) of this protocol and proceed to the post-treatment follow up period.

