7.2.2. Dose Adjustment for Renal Impairment

The dose adjustment for renal impairment will be managed by IWRS to ensure maintenance of the treatment blind. For patients randomized to active treatment during the originating studies, the eGFR value from the originating screening visit will be used by IWRS to assign the treatment doses accordingly. For patients randomized to placebo in the originating studies, the last available eGFR value from the originating study will be used by IWRS to assign the treatment doses accordingly.

- Patients with documented renal impairment (defined as eGFR ≥40 to <60 mL/min/1.73 m²), who are assigned to active treatment (either to the baricitinib 4-mg arm or the baricitinib 2-mg arm) will receive a baricitinib 2-mg QD dose by the IWRS.
- No dose adjustment will be made for patients with eGFR ≥60 mL/min/1.73 m².

The rationale of dose adjustment for patients with documented renal impairment is detailed in Section 5.4.

Interruption criteria due to eGFR during the treatment period is discussed in Section 8.1.1.

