Section 8.1.1 - Temporary Interruption of Investigational Product; Table JAIM.4 . Criteria for Temporary Interruption of Investigational Product	Delete interruption criterion based on eGFR <30.	Because of study blinding, “baseline” eGFR will not be known to investigators (For patients assigned to baricitinib in originating study, eGFR from baseline in the originating study is used. For patients assigned to placebo in originating study, eGFR from baseline in JAIM is used). The more conservative criteria (eGFR <40) will be used.
Section 9.4.6 - Hepatitis B Virus (HBV) DNA Monitoring	Text was modified to describe HBV monitoring every 6 months after W60.	Text was added to account for the increased interval of HBV testing after Week 60 due to the removal of study visits V8, V10, V12, and V14.
Section 10.3.1 – General Statistical Considerations	Text was updated to include efficacy and specify that integrated data will be assessed.	Updated to clarify that the safety and efficacy data would be (in addition to) assessed in the context of integrated data
Section 10.3.3 – Efficacy Analyses	Wording was updated to include the ANCOVA model.	ANCOVA model was needed to analyze SLICC/ACR responses.
Section 10.3.3.1 – Missing Data Imputation	Last Observation Carried Forward was changed to Modified Last Observation Carried Forward.	Text was changed to specify the methodology used in which to impute missing data.
Section 10.3.4 – Safety Analyses	Text added specifying how the endpoints of safety and tolerability would be analyzed and to outline safety measures to be reported specifically for JAIM.	To specify that the primary endpoints would be analyzed as a part of the integrated safety analyses for SLE and as such, will be reflected in the integrated safety analysis plan for SLE and to outline the categorical safety measures to be reported specifically for JAIM.
Section 10.3.4.1 – Adverse Events	PSAP analysis was removed	PSAP and iSAP are redundant terminology.
Section 10.3.4.3 - Vital Signs, Physical Findings, and Other Safety Evaluation	Text specifying that further analysis will be planned in the SAP iSAP was removed	Upon review of the section, the text was deemed unnecessary and was removed.

Revised Protocol Sections

Note: Deletions have been identified by striketroughs. Additions have been identified by the use of underscore.

1. Synopsis

Objectives and Endpoints

- | | |
|---|--|

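### The only eGFR hold rule in Table JAIM.4 is limited to patients with eGFR of at least 60, so patients treated at eGFR 40 to below 60 have no mandatory eGFR hold or resume criterion.

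*Protocol*

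**What the plan says.** Protocol Section 8.1.1 makes Table JAIM.4 binding: "Investigational product must be held in the following situations and may only be resumed as noted in the table". The table has nine rows, one of them on eGFR. That row requires a hold below 40 mL/min/1.73 m² "for patients with eGFR ≥ 60 mL/min/1.73" m², and allows resumption at 50 or above. Product interrupted for an abnormality outside the table "may be restarted at the discretion of the investigator".

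Section 7.2.2 provides for a renally impaired group: "Patients with documented renal impairment (defined as eGFR ≥40 to <60 mL/min/1.73" m²), who receive 2 mg whichever arm they are assigned to. It then points the reader on: "Interruption criteria due to eGFR during the treatment period is discussed in Section 8.1.1". Section 7.4 ties dose adjustment strictly to Sections 7.2.1 and 7.2.2, which use eGFR values from the originating study.

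Section 8.1.2 lists liver criteria and limits for white cells, neutrophils, lymphocytes and hemoglobin as grounds for permanent discontinuation. It has no eGFR limit.

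**The concern.** Section 7.2.2 promises eGFR interruption criteria for the treatment period, and the section it names has none for the patients it has just described. For them, both the hold and the restart are left to the investigator, and Section 8.1.1 recommends consulting the sponsor before interrupting for a reason outside the table.

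The result runs the wrong way round. Section 5.4 says that exposure rises as renal function falls, and the dose is not reduced for a fall during the study. Yet patients who start with impaired renal function have the weaker rule. After Week 60 the scheduled visits are 24 weeks apart (Weeks 60, 84, 108, 132 and 156) and retest timing is discretionary, so a hold that is not made at one visit may not come up again on schedule for about 24 weeks. Long-term safety is the primary objective of this trial.

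**Working it through.** The plan has no figure of its own to reproduce here. The check is one of coverage, followed by simple arithmetic on the resume value.

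**1. What the qualifier refers to.** A patient cannot be below 40 and at or above 60 at the same time, so the row must refer to some reference eGFR. It does not say which. The natural reading is the dose-assignment value in Section 7.2.2: originating-study screening eGFR for former baricitinib patients, and the last available originating-study eGFR for former placebo patients.

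**2. Mandatory eGFR rules by reference eGFR.**

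| Reference eGFR | Hold (8.1.1) | Resume (8.1.1) | Permanent stop (8.1.2) |
|---|---|---|---|
| 60 or above | below 40 | 50 or above | none |
| 40 to below 60 | none | none | none |

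Protocol Sections 5.1, 5.4 and 9.4 and SAP Section 5.4 contain no other eGFR hold, resume or stop rule.

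**3. Two patients on the same dose.** Both take 2 mg and both fall to eGFR 35. Patient A (reference at least 60) must be held and may resume only at 50 or above. Patient B (reference 40 to below 60) has no mandatory hold. The dose is the same, so the 2-mg cap does not explain the difference.

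**4. Effect of deleting the qualifier on the resume value.** Let e be the eGFR at entry. With resumption at 50, the rise needed above entry is 50 − e:
- e = 40: 50 − 40 = 10
- e = 45: 50 − 45 = 5
- e = 49: 50 − 49 = 1

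If resumption were instead allowed on return to the entry value, the margin over the hold limit would be e − 40, that is 0, 5 and 9, against 50 − 40 = 10 in the current row. All seven numeric rows of the table keep a gap between hold and resume:
- white cells: 2500 − 2000 = 500
- neutrophils: 1200 − 1000 = 200
- lymphocytes: 500 − 300 = 200
- platelets: 50,000 − 25,000 = 25,000
- eGFR: 50 − 40 = 10
- ALT or AST: 5 − 2 = 3 times the upper limit of normal
- hemoglobin: 9 − 8 = 1 g/dL

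**5. Who should be eligible for a lower resume value.** Suppose a lower value were tied to eGFR at JAIM Visit 1. A former baricitinib patient screened at 60 or above and taking 4 mg may have drifted to 45 by Visit 1. On the reading in step 1 this patient is covered now and must reach 50. A Visit 1 exception could let the patient restart 4 mg at 45, which is 5 units lower. Tying the exception to dose-assignment eGFR avoids this.

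**6. Size of the group.** Neither document gives the number of patients at 40 to below 60. SAP Appendix 2 plans a baseline split at 60, and SAP Section 6.2 plans a listing of assigned against received dose for patients below 60, so the sponsor can obtain a count.

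**The case against.** The strongest reply is that these patients are already protected. They are capped at 2 mg so that exposure stays within that of 4 mg at normal renal function (Section 5.4). Chemistry with eGFR is scheduled at Visits 1 to 11, early termination and Visit 801. Exclusion [4] lets the investigator keep out a patient whose laboratory values pose an unacceptable risk. The investigator may interrupt or stop product, and the medical monitor reviews laboratory trends (Section 9.4.8). All of this stands, so a reader who infers that the group is unprotected goes too far. None of it is a mandatory hold.

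It can also be said that a fall to 35 means less in someone who began at 40 (a fall of 5) than in someone who began at 60 (a fall of 25). That might argue for a different limit. It does not argue for having none, and the documents give no clinical reason for an exemption.

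Two stronger readings are tempting. One is that blinded investigators cannot apply the row at all. The rationale for the Section 8.1.1 change in Protocol Appendix 6 says that baseline "eGFR will not be known to investigators", and that "For patients assigned to placebo in originating study, eGFR from baseline in JAIM is used". But the operative row names no time point. The argument rests on the amendment rationale and affects only patients whose two candidate values lie on either side of 60. It is secondary. The other is that the table contradicts the amendment log. The log is not operative text and a difference from it is not an error. Its statement "The more conservative criteria (eGFR <40) will be used" serves only as evidence of intent: it suggests a leftover qualifier, not a deliberate exemption.

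**Conclusion.** The gap is real on the operative text of Sections 7.2.2, 8.1.1 and 8.1.2 alone: one mandatory eGFR hold rule for patients at 60 or above, none for patients treated at 40 to below 60. This rests on reading the qualifier as a reference value, which is the only reading that makes sense. The number of patients affected is unknown, and the documents do not show that anyone has been or would be harmed. The documents support calling this a missing mandatory rule in the group with prior renal impairment. They do not support calling it an absence of safeguards, or a dosing error. Correcting it is a cheap improvement.

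**What to change.** In Table JAIM.4, delete the qualifier on the eGFR row so that eGFR below 40 triggers a hold for every patient. Keep 50 or above as the resume value.

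Step 4 shows that 50 may be hard to reach for patients who entered between 40 and 49. If the sponsor wants a lower resume value for them, its medical team should set it, each use should need medical monitor agreement, and it should apply only to patients whose dose-assignment eGFR was 40 to below 60. The IWRS holds that value under blind. The present resume rule is then not loosened for 4-mg patients whose eGFR has since fallen.

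A check of Visit 1 eGFR before dosing is not proposed. Visit 1 should fall on the day of the originating study's final visit, product is provided then, and eGFR comes from the central laboratory with no provision for a same-day result. Sections 7.2.2 and SAP 5.4 need no rewording.

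Cost: one amended table row and, if wanted, a resume note. No new assessments and no change of analysis method. The downside is some more temporary holds in renally impaired patients. These count in the primary tolerability endpoint of temporary interruptions, and under SAP Section 6.2 patients assigned to 4 mg but dosed at 2 mg are counted in the 4-mg arm. If the change is made during the study, the report should give its date, because holds before and after it follow different rules.

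### No hold is required for ALT or AST >3 to 5 x ULN with raised bilirubin or INR while discontinuation is decided, and no restart rule is defined for such a hold

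*Protocol*

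**What the plan says.** Protocol 8.1.1 makes Table JAIM.4 binding: "Investigational product must be held in the following situations and may only be resumed as noted in the table". The table has one liver row. It requires a hold at ALT or AST >5 x ULN, and allows resumption once both are <2 x ULN, "possible DILI has been ruled out, and IP is not considered to be the cause of enzyme elevation". It has no row for bilirubin, INR or alkaline phosphatase (ALP), and none for a combination of tests.

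For interruptions outside the table, 8.1.1 says "It is recommended that the investigator consult with Lilly (or its designee) before temporarily interrupting therapy for reasons other than those defined in" the table, and that product interrupted for such a reason "may be restarted at the discretion of the investigator".

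Protocol 8.1.2 lists seven liver conditions. The third is "ALT or AST >3 x ULN and either total bilirubin level (TBL) >2 x ULN or international normalized ratio >1.5". For all seven, discontinuation should be "considered by the investigator when a patient meets one of the following conditions after consultation with the Lilly-designated medical monitor". A second list follows, of four hematology limits. Directly after it comes a paragraph which opens "Temporary interruption rules (see Section 8.1.1) must be followed where applicable" and continues "For lab values that meet permanent discontinuation thresholds, investigational product should be discontinued". That paragraph permits restart after medical monitor consultation if another cause is identified and the value has reached its Table JAIM.4 resumption threshold. The section then goes on to other circumstances such as pregnancy and malignancy.

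Protocol 9.4.7 calls for a repeat liver panel within 3 to 5 days once ALT reaches 3 x ULN, or ALP or bilirubin reaches 2 x ULN. If the abnormality persists or worsens, it calls for monitoring in consultation with the medical monitor until levels normalize or come back near baseline. Appendix 4 lists further tests that may be obtained.

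**The concern.** An enzyme rise together with raised bilirubin or INR suggests that liver function is affected. The protocol treats it as serious enough for the permanent-discontinuation list. Yet an isolated ALT of 5.5 x ULN triggers a compulsory hold, while ALT 4 x ULN with bilirubin 2.5 x ULN does not.

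A site with the second patient needs to know whether tomorrow's dose is taken while the medical monitor is consulted and the repeat panel is awaited. The protocol does not say. Patients have the tablets at home: 7.1.1 supplies enough for the longest interval between visits, and after Week 60 the scheduled visits are 24 weeks apart. Two sites could therefore handle the same patient differently. Section 3.3 names hepatotoxicity as an important potential risk. Temporary interruptions and permanent discontinuations are also part of the primary endpoint, so differing practice would affect what is counted as well as patient safety.

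**Working it through.** No sample size, power or event figure is involved. The check sets the rules side by side.

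**1. Liver conditions in 8.1.2 against the Table JAIM.4 liver row (ALT or AST >5 x ULN)**

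| Condition in 8.1.2 | Inside the hold row? |
|---|---|
| 1. ALT/AST >8 x ULN | Always |
| 2. ALT/AST >5 x ULN for over 2 weeks after interruption | Always (already held) |
| 3. ALT/AST >3 x ULN with bilirubin >2 x ULN or INR >1.5 | Only if ALT/AST >5 x ULN |
| 4. ALT/AST >3 x ULN with symptoms or eosinophilia | Only if ALT/AST >5 x ULN |
| 5. ALP >3 x ULN | No row |
| 6. ALP >2.5 x ULN with bilirubin >2 x ULN | No row |
| 7. ALP >2.5 x ULN with symptoms or eosinophilia | No row |

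Always inside: 2 of 7. Only above 5 x ULN: 2 of 7. No row: 3 of 7. This point concerns condition 3 when ALT or AST is >3 to 5 x ULN.

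**2. Does other text require a hold?**

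- The instruction in 8.1.2 to follow the interruption rules leads back to Table JAIM.4, which has no row for this patient.
- Section 9.4.7 requires retesting and monitoring but is silent on dosing meanwhile. It refers to Section 8.1 for interruption or discontinuation criteria on ALT, AST, bilirubin and ALP; Table JAIM.4 contains no bilirubin or ALP criterion.
- Appendix 4 concerns tests only.

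**3. What governs restart?**

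- The stop and restart paragraph in 8.1.2 directly follows the hematology list. It refers to Table JAIM.4 thresholds, which all four hematology limits have. The liver list already has its own instruction, that discontinuation be considered. The paragraph therefore most naturally covers the hematology list only.
- Restart after an off-table liver hold then falls under 8.1.1, at the investigator's discretion. The conditions in the >5 x ULN row, including that drug-induced liver injury be ruled out, do not apply.
- Of the three tests in condition 3, Table JAIM.4 gives a resumption threshold for ALT/AST but not for bilirubin or INR: 1 of 3.

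**4. Is INR available?** It is named neither in the routine panel (Appendix 2) nor in the 9.4.7 repeat list, only among the optional Appendix 4 tests. A hold rule can use it only where it has been measured.

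**5. Hematology for comparison.** WBC <1000 lies inside the hold at <2000; neutrophils <500 inside <1000; lymphocytes <200 inside <300; hemoglobin <6.5 inside <8. That is 4 of 4.

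**The case against.** The strongest reply is that the protocol leaves this decision to clinical judgement on purpose and surrounds it with controls. Nothing prevents an immediate hold: sponsor consultation before an off-table interruption is only recommended, and 8.1.2 lets the investigator stop product at any time. No waiting period is set before the discontinuation decision. Under 9.4.7 the medical monitor is involved if the abnormality persists, so a discretionary restart would seldom be a decision made alone. Section 3.3 reports no severe drug-induced liver injury to date. All of this stands, and it limits the size of the point. None of it requires dosing to stop in the interval, or sets a condition for resuming.

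It can also be objected that 4 of 4 against 2 of 7 describes layout and does not measure risk. That is right: Table JAIM.4 has platelet and eGFR rows with no counterpart in 8.1.2, so the two lists were not built to mirror each other. The comparison shows only where a required hold is absent.

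A reader might infer that 8.1.2 contradicts itself, telling the investigator both to consider discontinuing and to discontinue. The documents do not support this, since the second instruction most naturally belongs to the hematology list. If it did cover liver tests, dosing would stop and the missing hold would matter much less. Restart would then rest on thresholds that do not exist for bilirubin or INR.

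**Conclusion.** The gap is real and narrow. For ALT or AST >3 to 5 x ULN with bilirubin >2 x ULN or INR >1.5, the protocol requires no hold while discontinuation is being decided and defines no restart rule after a voluntary hold. A reader might go further and infer that such patients are unprotected or would go on dosing. The text does not support that, given the controls in 8.1.1, 8.1.2 and 9.4.7.

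The absence of the hold row is plain on the text. The conclusion about restart assumes that the stop and restart paragraph in 8.1.2 covers only the hematology list; this is inferred from its position and fit, because the protocol does not state its scope. The documents do not give the number of patients who would meet the criterion, and none is estimated here. The change is worth making because it is cheap and safer, not because the trial's conclusions depend on it.

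**What to change.** Add one row to Table JAIM.4 by amendment.

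- **Hold:** ALT or AST >3 x ULN with either bilirubin >2 x ULN (known Gilbert's syndrome excepted, as 9.4.7 does for data collection) or, where measured and not explained by anticoagulant treatment, INR >1.5. The hold lasts until the discontinuation decision is made.
- **Resume:** only after medical monitor consultation, with ALT and AST <2 x ULN, bilirubin (and INR if measured) below the trigger, possible drug-induced liver injury ruled out, and product not considered the cause.

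A sentence in 8.1.2 limiting the stop and restart paragraph to the hematology list would be a useful editorial clarification, but is optional.

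The other four conditions without an assured hold (4 to 7 in the table above) are outside this fix. For the two symptom-based ones there is a reason: fatigue, fever and rash are also features of SLE (3.2). That reason does not extend to the two ALP conditions without symptoms, which the sponsor would need to consider separately.

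The cost is one table row and a few more temporary interruptions, which would count in the interruption endpoint. No scheduled test is added.
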